7.2.2. Weight and Height

The subject's body weight will be measured using a calibrated balance. Body weight will be recorded with 1 decimal. The subject's height is measured without wearing shoes. The BMI will be calculated from the weight and height recorded during the Screening Period (based on the following formula):

BMI (kg/m²)=weight (kg)/height² (m²).

7.2.3. Physical Examination

A complete physical examination will be performed at Screening Period, and a targeted physical examination will be performed in the remainder of the visits. Clinically relevant findings that are observed prior to the Screening Period assessment must be recorded on the relevant Medical History eCRF section. Clinically relevant findings found after study drug initiation and meeting the definition of an AE (new AE or worsening of previously existing condition) must be recorded on the AE section of the eCRF.

7.2.4. 12-Lead Electrocardiogram

The predose 12-lead ECG assessment will be performed prior to administration of the study drug at the clinic visit. In subjects in the PK Sub-Study, an additional 12-lead ECG will be taken at approximately 4 and 8 hours after administration of study drug. Additional ECGs may be taken at any other times if deemed necessary by the PI or designee. Subjects should be resting for at least 5 minutes in supine position prior to ECG procedures.

All ECG tracings will be reviewed by the PI or designee. ECGs will be evaluated and classified as normal/abnormal. In case of "abnormal," the abnormality must be described and its relevance in terms of clinical significance documented.

7.2.5. Clinical Laboratory Assessments

Blood samples will be taken under fasted conditions. Subjects will not be allowed to eat for a period of 8 hours prior to blood sampling or drink (except water) for a period of 4 hours prior to blood sampling.

All clinical laboratory tests listed in Table 5 will be performed as outlined in the Schedule of Assessments (Table 1 and Table 2). In addition, laboratory safety tests may be performed at various unscheduled timepoints if deemed necessary by the PI or designee.

Clinically significant laboratory abnormalities must be reported by the investigator as an AE or SAE as appropriate.

The results of all laboratory tests will be provided to the investigator in order for the investigation to make an assessment of clinical significance, with the exception of the lipid (cholesterol [total], low-density lipoprotein [LDL], high-density lipoprotein [HDL], triglycerides, apolipoprotein A, apolipoprotein B), amylase, and lipase values. The lipid, amylase, and lipase values (both individual subjects and study level) will be monitored regularly for the entirety of the study by the DSMB.

Table 5: Summary of Clinical Laboratory Tests

| Hematology | Chemistry | Urinalysis | Others |
|-------------------------|------------------------------------|------------------|----------------------|
| Hemoglobin | Urea | Urobilinogen | Serum/urine |
| Hematocrit | Creatinine | Nitrite | pregnancy test |
| RBC count | Fasting glucose | pН | (β-HCG) ^b |
| Reticulocytes | Sodium | Glucose | FSH |
| Platelet count | Potassium | Total protein | Coagulation (PT |
| WBC count | ALT | Erythrocytes | [sec], PT [INR], |
| Neutrophils | AST | Leukocytes | aPTT) |
| Eosinophils | GGT | Ketones | |
| Monocytes | Bilirubin (total, direct/indirect) | Microscopya | |
| Basophils | Alkaline phosphatase | Specific gravity | |
| Lymphocytes | Albumin | Bilirubin | |
| Mean corpuscular volume | Cholesterol (total) | | |
| | LDL | | |
| | HDL | | |
| | Triglycerides | | |
| | LDH | | |
| | Amylase | | |
| | Lipase | | |
| | Apolipoprotein A | | |
| | Apolipoprotein B | | |

Abbreviations: β-HCG, beta human chorionic gonadotropin; ALT, alanine aminotransferase; aPTT, activated partial thromboplastin time; AST, aspartate aminotransferase; FSH, follicle-stimulating hormone:

GGT, gamma-glutamyltransferase; HDL, high-density lipoprotein; INR, international normalized ratio; LDH, lactate dehydrogenase; LDL, low-density lipoprotein; PCR, polymerase chain reaction; PT, prothrombin time; RBC, red blood cell; SARS-CoV-2, severe acute respiratory syndrome coronavirus 2; WBC, white blood cell

^a Urine sediment examination will only be performed if there is an abnormality in urinalysis in accordance with clinical laboratory standard procedures.

^b Required for all female subjects.

Note: Nasal and throat mucosal cell samples will be collected according to work instructions detailed in the site-specific manual. The samples will be tested for SARS-CoV-2 virus using PCR tests.

7.2.6. Pregnancy Test

Serum pregnancy tests (beta human chorionic gonadotropin [β -HCG]) will be performed at Screening. Urine pregnancy tests will be used for all other scheduled visits. If a urine pregnancy test is positive, a serum pregnancy test will be conducted for confirmation and dosing should be immediately suspended and evaluated for continued study participation based upon the result of the serum pregnancy test and in discussion with the medical monitor. Urine pregnancy test results should be available immediately to site. The results must be available prior to dosing (Table 1, Table 2, and Table 3).

7.2.7. Columbia-Suicide Severity Rating Scale

The C-SSRS is a questionnaire that prospectively assesses suicidal ideation and suicidal behavior. The C-SSRS, which uses a semi-structured interview to probe subject responses, will be administered by an individual who has received training and certification in its administration. During the Screening Visit (Day -56), the "baseline" version of the C-SSRS will be administered. This version assesses suicidal ideation and suicidal behavior during the subject's lifetime and during a predefined period. At all subsequent visits, the "since last visit" version will be administered.

7.2.8. Breast Cancer Imaging Surveillance

Mammograms will be performed for female subjects only. If clinically indicated, an ultrasound or MRI may also be conducted for breast cancer imaging, per the investigator's discretion.

7.3. Adverse Events, Serious Adverse Events, and Other Safety Reporting

7.3.1. Definition of Adverse Events

An AE is an untoward medical occurrence associated with the use of a study intervention in humans, whether or not it is considered related to the study intervention. An AE can therefore be any unfavorable and unintended sign (for example, an abnormal laboratory findings), symptom, or disease in a study subject who is administered with study intervention in this study.

Below are the criteria for the events that meet and do NOT meet the definition of an AE:

Events Meeting the Adverse Event Definition

- All AEs during the course of treatment with study intervention.
- All AEs resulting from medication misuse, abuse, withdrawal, or overdose of study intervention.
- All AEs resulting from medication errors such as dispensing or administration error outside of what is described in the protocol.
- Apparent unrelated illnesses, including worsening of a preexisting illness.
- Injury or accidents. Note that if a medical condition is known to have caused the injury or accident (a fall secondary to dizziness), the medical condition (dizziness)

- and the accident (fall) should be reported as 2 separate AEs. The outcome of the accident (hip fracture secondary to the fall) should be recorded in source documents.
- Abnormalities in physiological testing or physical examination findings that require clinical intervention or further investigation (beyond ordering a repeat [confirmatory] test).
- Laboratory or ECG abnormalities that require clinical intervention or further investigation (beyond ordering a repeat [confirmatory] test) unless they are associated with an already reported clinical event.

Events NOT Meeting the Adverse Event Definition

- Laboratory abnormalities associated with a clinical event should be captured in the source documents. Laboratory abnormalities not requiring clinical intervention or further investigation will be captured as part of overall laboratory monitoring and should not be reported as AEs.
- The disease/disorder being studied or expected progression, signs, or symptoms of the disease/disorder being studies, unless more severe than expected for the subject's conditions (see Section 7.3.11).
- Preexisting conditions (eg, allergic rhinitis) must be noted in the eCRF at Screening but should not be reported as AEs unless the medical condition worsens, or episodes increase in frequency during the AE reporting period.
- Diagnostic and therapeutic noninvasive and invasive procedures, such as surgery, should not be reported as AEs unless the medical condition for which the procedure was performed meets the definition of an AE. For example, an acute appendicitis that occurs during treatment with the study drug should be reported as the AE, and the resulting appendectomy should be recorded in the source documents and eCRF. If a surgical procedure was planned prior to entry into the study, and the surgery is not performed because of a worsening of a baseline condition, this should not be reported as an AE. Note that, as described in Section 7.3.2, any hospitalization occurring as the consequence of an AE during the study period should be reported as an SAE.

Each AE is to be classified as serious or nonserious by the investigator using medical and scientific judgment.

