1.4. Findings From Nonclinical and Clinical Studies

1.4.1. Nonclinical Studies

Nonclinical pharmacodynamic (PD) studies on PTC857 completed to date include 1 enzyme inhibition study, 4 cell pharmacology studies, 1 in vivo PK/PD study, and 2 in vivo efficacy studies. The findings of nonclinical pharmacology studies support the clinical development of PTC857 in neurodegenerative diseases such as ALS.

Results from an in vitro study evaluating the protective activity and potency of PTC857 against ferroptotic cell death in human spinal astrocytes demonstrated that PTC857 prevented RAS-selective lethal compound 3-induced ferroptotic cell death and was 70-fold more potent than edaravone, and riluzole conferred no protection at preventing ferroptotic cell death.

Nonclinical pharmacology studies have demonstrated protection of the neuromuscular junction in an animal model of ALS. In an in vivo study evaluating the efficacy of PTC857 in the SOD1*G93A mouse model of ALS, PTC857 was demonstrated to protect innervation of the neuromuscular junction. In a second study, PTC857 improved grip strength and delayed morbidity of SOD1*G93A mice.

Safety pharmacology studies were conducted in Sprague Dawley rats to assess the effects of PTC857 on respiratory and neurobehavioral function. The effect of PTC857 on cardiovascular (CV) function was assessed in a single-dose study conducted in cynomolgus (CNG) monkeys and in 1-, 3-, and 9-month repeat-dose monkey GLP toxicity studies. These safety pharmacology studies did not identify any risk factors for the administration of PTC857 in subjects.

PTC857 was neither mutagenic nor clastogenic in 2 in vitro (bacterial reverse mutation test and TK6 cell in vitro micronucleus test) and 1 in vivo (rat micronucleus test) genotoxicity studies.

One- and 3-month repeat-dose GLP toxicology studies were conducted in rats and monkeys with PTC857. In the 1-month rat toxicology study, rats were orally administered PTC857 at doses of 0, 100, 300, and 1000 mg/kg/day. The dose-limiting PTC857-associated toxicities observed in the 1-month rat study included moderate increases in prothrombin time in males at 1000 mg/kg/day and microscopic changes in the stomach in both sexes at ≥300 mg/kg/day. Changes in the stomach included mild to moderate submucosal edema, which was observed in non-glandular and glandular sections of the stomach in conjunction with adverse findings in the

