7.3.3. Adverse Events Reporting

AEs will be reported by the subjects (or, when appropriate, by a caregiver, surrogate, or the subject's legally authorized representative).

The investigator and any qualified designees are responsible for detecting, documenting, and recording events that meet the definition of an AE or SAE and remain responsible to pursue and obtain adequate information both to determine the outcome and to assess whether the event meets the criteria for classification as an SAE or caused the subject to discontinue the study intervention (see Section 6.1).

Each subject/parent(s)/legal guardian will be questioned about the occurrence of AEs in a nonleading manner.

In addition, the investigator may be requested by the PTC Pharmacovigilance Department to obtain specific follow-up information in an expedited fashion.

All AEs are to be recorded in the source documents and on the eCRF using concise medical terminology; whenever possible, terms contained in the Medical Dictionary for Regulatory

Activities (MedDRA) should be employed. In addition, the following information should be recorded:

- Indication of whether the event is serious or nonserious (see Section 7.3.2)
- Relationship to study intervention (see Section 7.3.5)
- Severity of the event (see Section 7.3.5)
- Onset date
- Resolution date, or date of death
- Action taken
- Outcome of the event

Table 6 below summarizes the investigator site requirements for recording AEs on the eCRF and for reporting SAEs, adverse events of special interest (AESI) on the SAE Report Form to the PTC Pharmacovigilance Department.

Table 6: Investigator Site Requirements for Recording/Reporting Adverse Events

| Event | Recorded on the eCRF | Reported to the PTC Pharmacovigilance Department Within 24 Hours of Awareness |
|----------------------------------|-------------------------|---|
| Serious AE | All | All |
| Nonserious AE | All | None |
| Other, eg, exposure to the study | All (regardless of | All |
| intervention during pregnancy or | whether associated with | (regardless of whether associated with |
| breastfeeding | an AE) | an AE) |
| AESI | Not applicable | Not applicable |

Abbreviations: AE, adverse event, AESI, adverse event of special interest, eCRF, electronic care report form

7.3.4. Time Period and Frequency for Collecting Adverse Event and Serious Adverse Event Information

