6.2.2. Adverse Events Indicative of ALS Disease Progression

TEAEs that are indicative of ALS disease progression will be tabulated by treatment arm. The following list of MedDRA preferred terms will be used to define TEAEs that are indicative of disease progression.

Acute respiratory failure	Increased bronchial secretion	Salivary hypersecretion
Affect lability	Increased upper airway secretion	Suicidal ideation
Amyotrophic lateral sclerosis	Muscle spasms	Upper respiratory tract infection
Asthenia	Muscle spasticity	Urge incontinence
Balance disorder	Muscular weakness	Urinary retention
Cardio-respiratory arrest	Musculoskeletal stiffness	Urinary tract infection in males
Death	Myalgia	Urinary tract inflammation in males
Dysgraphia	Neurogenic bladder	Viral upper respiratory tract infection
Dysphagia	Oral candidiasis	Vocal cord paralysis
Dyspnoea	Oral fungal infection	Weight decreased
• Fall	Respiratory failure	
Fatigue	Respiratory tract congestion	
Hypotonia	Respiratory tract infection	
Hypoxia	Respiratory tract infection viral	

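### Protocol 7.3.1 sends the injury that results from an accident to source documents, so the injury gets no adverse-event term, grade or causality of its own

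*Protocol*

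**What the plan says.** Protocol 7.3.1, under events that meet the AE definition, has a bullet that begins "Injury or accidents. Note that if a medical condition is known to have caused the injury or accident". It takes a fall caused by dizziness as its example. The dizziness "and the accident (fall) should be reported as 2 separate AEs". The bullet then deals with the injury: "The outcome of the accident (hip fracture secondary to the fall) should be recorded in source documents".

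Protocol 7.3.3 gives the general rule: "All AEs are to be recorded in the source documents and on the eCRF". It also lists what is captured for each AE, including seriousness, relationship to study drug, severity and outcome.

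On surgery planned before study entry, 7.3.1 says that if "the surgery is not performed because of a worsening of a baseline condition, this should not be reported as an AE". The same section lists among reportable events "Apparent unrelated illnesses, including worsening of a preexisting illness".

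SAP 6.2 (Part A) tabulates treatment-emergent events by system organ class and preferred term, with further tables by severity, relationship and seriousness. Section 6.3.1 of the SAP for Parts B and C does the same for the extension periods.

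**The concern.** In the example the fracture is the medically most important part, yet it is the one part not directed to the AE page. If sites apply the example as written, an injury exists in the trial database only as a fall and the condition that caused it. It has no coded term, no grade and no causality assessment of its own.

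The severity and number of TEAEs and TESAEs form a secondary endpoint for Part A (Protocol 2.2.2) and an endpoint for each extension period (2.2.4 and 2.2.5). Falls are an expected kind of event in a progressive motor disease. A reader of the safety tables would want to tell a fall without consequence from one with a fracture or head injury, and to compare such injuries between arms. The tables cannot show that if the injury was never entered.

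**Working it through.** No arithmetic applies: the documents give no figure on this point. The check is a comparison of texts.

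**The injury rule**

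| Place | What it directs |
|---|---|
| 7.3.1, opening of the injury bullet | Injury meets the AE definition |
| 7.3.1, example in that bullet | Two AEs, the condition and the accident; the fracture goes to source documents |
| 7.3.1, appendectomy example | The procedure goes to source documents and also to the eCRF |
| 7.3.1, laboratory findings tied to a clinical event | Source documents; listed among events that are not AEs |
| 7.3.3 | Every AE goes to source documents and the eCRF |

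1. The example fixes the number of AEs at two, and the fracture is neither of them.
2. The word *only* does not appear, so source-documents-only is an inference. Two places in the section support it. The appendectomy example names the eCRF where eCRF capture is wanted. The laboratory bullet uses source-document capture for findings that are not AEs.
3. On that reading the example contradicts the opening of its own bullet. If the injury is an AE, 7.3.3 puts it on the eCRF.
4. It also fits poorly with 7.3.2, which wants the event that caused a death to be the reported AE. After a fatal accident that event may be the injury.
5. The SAP tables are built from reported events. An injury that was not entered as an AE has no preferred term to count and no grade or relationship to tabulate.

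**The planned-surgery sentence**

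It can be read in two ways.

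- The surgery is cancelled because the condition worsened, and *this* is not an AE. Even then, *this* may mean the cancelled procedure and not the worsening.
- The surgery is carried out, but not because of worsening, so the planned procedure is not an AE. This suits a bullet about procedures, which opens by excluding them unless the underlying condition is itself an AE.

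Three other statements make worsening reportable: the illness bullet quoted above, the pre-existing-conditions bullet in 7.3.1, and 7.2.3, which sends a worsened existing condition to the AE section of the eCRF. The sentence is therefore ambiguous, and it contradicts those three statements on one reading only.

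**The case against.** The best case for leaving the text alone is that little is lost. The injury bullet sits under events that meet the AE definition, and nothing forbids entering the fracture. The fall is itself an AE, graded at the highest severity reached (7.3.5.1). Any hospitalization that follows from an AE makes it an SAE (7.3.1). Disability and medical importance are further routes to seriousness (7.3.2), and SAEs are reported within 24 hours (7.3.4.1). A fall with a hospitalized hip fracture would therefore still count in the TEAE and serious TEAE tables. The rule applies equally to both blinded arms and touches no efficacy result.

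Most of this stands. The accident is counted, and its seriousness is usually captured. What does not stand is that the injury is captured as an injury. Even when the event is an SAE, its term would be the fall. An injury that meets no seriousness criterion leaves no trace beyond the grade of the fall. Section 7.3.2 also exempts hospitalizations related only to disease progression, a judgement that may arise for falls in ALS.

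**Conclusion.** The point holds as a gap in data capture. Followed as written, Protocol 7.3.1 leaves an injury from a medically caused accident without a preferred term, grade or causality of its own in the TEAE and TESAE tables. This assumes that sites take the example literally, which the appendectomy wording makes likely. How many injuries are affected cannot be stated: the documents give no rate of falls, of injuries among fallers, or of falls with a known medical cause. The planned-surgery sentence is a minor wording matter.

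A reader might infer four stronger conclusions, which the documents do not support.

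- *Serious injuries disappear from the safety tables.* The fall remains, graded, and is serious when hospitalization follows.
- *The SAP relabels injuries as disease progression.* Fall is among the terms in Part A SAP 6.2.2, where "TEAEs that are indicative of ALS disease progression will be tabulated by treatment arm". The revision history describes this as an additional summary, and it removes nothing from the main tables in 6.2. No change to 6.2.2 is needed.
- *A coagulation effect could be hidden.* Protocol 1.4.1 reports "moderate increases in prothrombin time in males at 1000 mg/kg/day", in a 1-month rat study with a no-adverse-effect level of 100 mg/kg/day. Prothrombin time, INR and aPTT are measured directly in the trial (Table 5), and bleeding not caused by an accident is unaffected by this rule. The link is speculative.
- *Worsening that cancels surgery is excluded from the AE data.* The sentence does not plainly say so, and three other statements say that worsening is reportable.

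**What to change.** In Protocol 7.3.1, replace the sentence on the outcome of the accident. State that an injury resulting from an accident is recorded as its own AE on the eCRF, with its own term, grade and seriousness, in addition to the accident and its cause. Causality then follows from 7.3.3 and 7.3.5.2, which apply to every AE. Carry the same instruction into the eCRF guidance. For subjects already treated, injuries noted in source documents could be checked against the eCRF before database lock.

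As a minor edit, reword the planned-surgery sentence to agree with 7.2.3 and the rest of 7.3.1: the planned or cancelled procedure is not itself an AE, and any worsening of the condition is reported.

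The cost is two sentences, a note to sites and, if done, some monitoring time. There will be a few more AE records, and injury counts will be slightly higher.

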7.3.2. Definition of Serious Adverse Event

An SAE is an untoward medical occurrence or effect at any dose, regardless of whether it is related to the study intervention, which results in one of the following:

• Results in death. This includes all deaths on treatment or within 30 days after last study intervention administration, including deaths due to disease progression. Any death occurring later than 30 days following the last dose need not be reported as an SAE unless it is a result of an event that started within the period covered by the onstudy definition. The reported AE should be the event that caused the death. In addition, any AE resulting in death that occurs post the AE reporting period and that

the investigator assesses as possibly related to the study intervention should also be reported as serious.

- Is life-threatening. This refers to an event in which the subject was at risk of death at the time of the event. It does not include an event that, had it occurred in a more severe form, hypothetically might have caused death.
- Requires hospitalization or prolongation of existing hospitalization (excluding
 hospitalizations for administration of the study intervention, procedures required by
 the study protocol, or treatment-related diagnostic procedures; other planned
 hospitalizations; or hospitalizations related only to progression of disease).
 Emergency room visits that do not require admission to the hospital do not fall into
 this category, but the event may be serious due to another seriousness criterion.
- Results in persistent or significant disability or incapacity or substantial disruption of the ability to conduct normal life functions.
- Any other medically important event that the investigator or PTC judges to be serious or which is defined as serious by the regulatory agency in the local country. These are AEs that might not be immediately life-threatening or result in death or hospitalization but might jeopardize the subject or might require intervention to prevent one of the other outcomes listed above. Medical judgment should be exercised in deciding whether an AE is serious based on the above definition. Examples of such events are intensive treatment in an emergency room or at home for allergic bronchospasm, blood dyscrasias or convulsions that do not result in hospitalization, or development of drug dependency or drug abuse.
- A pregnancy resulting in spontaneous abortion, stillbirth, neonatal death, or congenital anomaly (including that in an aborted fetus).

Note: Hospitalization for social circumstances without any other accompanying SAE should not be reported as an SAE.

